To achieve this second Aim we will conduct an additional, third 8-hour study arm with the iLet BP using Xeris glucagon, which will be compared to the 8-hour study arm with the iLet BP using Lilly glucagon. The data from Aim 1 will be analyzed prior to initiation of the Aim 2 visit. If the performance of the iLet BP in the studies of Aim 1 visits is as expected, we will proceed to the visits of Aim 2. Subjects will arrive fasting and remain fasted until the lunch meal. They will exercise on a stationary bike bpm for approximately 30 minutes with a heart rate from 120–140, starting at least 2 hours after lunch. The primary outcome will be the average percent of glucagon calculated by the control algorithm that is successfully delivered by the pump. Important secondary outcomes will include infusion site reactions at the glucagon site, subject reported nausea, glucagon exposure (plasma insulin and glucagon levels will be measured every 30 minutes throughout the experiment), and measures of glycemic regulation, including mean CGM glucose and hypoglycemia exposure (% time <60 mg/dl).

Aim 3. To document the satisfaction of subjects with the iLet BP device with the goal of optimizing user interaction with the iLet.

Questionnaires will be administered at the beginning of the study and at the end of each arm to gather data on attitudes towards bionic pancreas usability, BG control, quality of life and treatment satisfaction. The primary analysis will include data from the first 2 arms (iPhone BP and iLet BP with Lilly glucagon) so that the analysis will be focused entirely on the performance of the BP platform and not the glucagon. A structured phone interview will be conducted with each participant after they have completed all of the visits to compare their experiences. This information will be used to make the best choices about how the final version of the bionic pancreas should be configured.

Aim 4. To conduct an in-clinic study comparing the performance of an investigational infusion set designed for use with the iLet Bionic Pancreas versus an FDA approved infusion set in up to 10 adult subjects with type 1 diabetes in both the fasted and post-prandial states.

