- Once all of the results have been returned, a study MD will review the case report form to determine subject eligibility. If subjects are not eligible to continue in the study the results of abnormal tests will be reported to the subjects and to a health care provider of their choosing.
- Subjects who have been screened and are eligible can participate without having to be re-screened for a period of one year. The study staff should verbally confirm that there have been no health events that would make them ineligible if the interval between screening and participation is longer than 3 months.
- Subjects who participated in Aim 1 and/or Aim 2 will be eligible to participate in Aim 4, but will have to be rescreened if it has been more than 1 year.

V. d. 2. Visit Order: Once the subject has been enrolled and eligibility of subjects has been established, the order of the visits using Lilly glucagon with the iPhone based system and the iLet system will be randomized in blocks of two subjects. The experiments of Aim 2 (iLet BP with Xeris glucagon) will be performed after the first two visits.

The order of the visits for the Infusion Set Sub-Study of Aim 4 will be randomized in blocks of two subjects, separately from the visits for Aim 1 and Aim 2.

V. d. 3. Training Visit: A training visit will take place before the first bionic pancreas visit. Subjects will be

trained in the insertion and calibration of the Dexcom G4 sensor, insertion of infusion sets, use of the two bionic pancreas systems and study policies and procedures. Study staff will verify that the subjects have understood the material and are competent to participate safely in the study.

A training visit is not required for the Infusion Set Sub-Study.

V. d. 4. Bionic Pancreas Visits

- Up to 2 subjects may participate at the same time.
- Each subject will participate in the bionic pancreas visit three times: once with the iPhone-based BP, once with the iLet BP using Lilly glucagon and once with the iLet BP using Xeris glucagon.
- The night before the visit, subjects will place a Dexcom G4 CGM sensor that is provided by the study team, and calibrate the sensor when prompted using the provided Nova Biomedical Statstrip Xpress meter. Subjects will be instructed to call if they encounter any difficulty with their CGM.

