- After approximately 3-4 hours of closed loop control, the subjects will be permitted to eat lunch. The content of their meal will not be restricted in any way, with the exception that the number of carbohydrates should be in the "typical" range for them at lunch, and that they must eat the same meal at approximately the same time during both visits. Practically speaking, this means that they must have the same lunch that can be delivered or brought to the DRC. Subjects will select meals that will have a typical amount of carbohydrates for a lunch-time meal and will announce their meals to the bionic pancreas by selecting the "typical" option in the meal announcement screen.
- After lunch is completed, the subjects will not be allowed any carbohydrate intake (non-caloric drinks will be permitted) until the study is completed, to allow the bionic pancreas to control the post-prandial blood glucose without further interruption.
- Approximately 2 hours after lunch is completed (Hour 5-6 of the experiment), subjects will exercise on a stationary bike with a heart rate from 120-140 beats per minute (bpm) for a total of 4,000 heart beats (approximately 30 minutes). Subjects will rate their exercise intensity using the Borg scale every 5 minutes, with the target intensity level between 12 and 14. Heart rate will be measured every 5 minutes.
- BG measurements using the YSI will be obtained off of the IV line every 10 minutes during exercise. If the BG is < 80 mg/dl, BG measurements will be obtained off of the IV line every 5 minutes.
 - Carbohydrates will be given for any BG < 50 mg/dl according to the following protocol: Dextrose (g) = $BSA (m^2) / [1.7 m^2 (women) \text{ or } 1.9 m^2 (men)] * 15g$
 - Repeat treatments will be given at 15 minute intervals as long as BG remains < 50 mg/dl.
 - Heart rate will be measured every 5 minutes during exercise
 - Subjects will be asked to rate the intensity of their exercise every 5 minutes using the Borg Scale

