Financial compensation will be provided to all subjects who complete the screening visit. Subjects will be paid \$25 for completing the screening visit whether or not they are eligible to participate in the study. Study participants will be compensated \$150 for completing the three study visits. Thus the total compensation for a subject who completed the study would be \$175. Parking expenses will be paid for up to \$30 per subject, and lunches will be paid for up to \$100 per subject (50 dollars per lunch). Subjects who are unable to complete the study or chose to stop participation will receive prorated compensation at a rate of \$50 per completed day. In addition to the monetary compensation, the cost of the subjects lunch meals during their participation in the study will be covered by study funds.

X. a. Infusion Set Sub-Study Compensation:

Financial compensation will be provided to all subjects who complete the screening visit. Subjects will be paid \$25 for completing the screening visit whether or not they are eligible to participate in the study. Study participants will be compensated \$50 for completing each study visit. Thus the total compensation for a subject who completed the study would be \$125. Parking expenses will be paid for up to \$30 per subject, and breakfast will be paid for up to \$40 per subject (20 dollars per meal).

XI. References

1. The Diabetes Control and Complications Trial research Group (DCCT) (1993) The effect of intensive treatment of diabetes on the development and progression of long-term complications in insulin dependent diabetes mellitus. *N. Engl. J. Med.* 329, 977–986.
2. The Diabetes Control and Complications Trial/Epidemiology of Diabetes Interventions and Complications (DCCT/EDIC) Study Research Group (2005) Intensive Diabetes Treatment and Cardiovascular Disease in Patients with Type 1 Diabetes. *N. Engl. J. Med.* 353, 2643–2653.
3. El-Khatib, F. H., Jiang, J., Gerrity, R. G. & Damiano, E. R. (2007) Pharmacodynamics and stability of subcutaneously infused glucagon in a type 1 diabetic swine model in vivo. *Diabetes Technol. & Ther.* 9, 135-144
4. El-Khatib, F. H., Jiang, J. & Damiano, E. R. (2007) Adaptive closed-loop control provides blood-glucose regulation in vivo using dual subcutaneous of insulin and glucagon infusion *Diabetes Sci. & Technol.* 2, 181-192.

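### The same-lunch rule covers two visits and was not extended to the third (Xeris) visit, so the meal-sensitive secondary outcomes of Aim 2 lack it on one side

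*Combined protocol and SAP*

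**What the plan says.** Section V.d.4 (Bionic Pancreas Visits) states: "Each subject will participate in the bionic pancreas visit three times". These are the iPhone-based system, the iLet with Lilly glucagon and the iLet with Xeris glucagon. Under Visit Procedures in the same section, the only rule that matches lunch between visits says of subjects that "they must eat the same meal at approximately the same time during both visits". The following sentence draws the practical consequence, an identical lunch that can be brought to the research center, without naming a number of visits.

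On Aim 2, Section II describes the third arm as one "which will be compared to the 8-hour study arm with the iLet BP using Lilly glucagon". Section V.d.2 fixes its position: "The experiments of Aim 2 (iLet BP with Xeris glucagon) will be performed after the first two visits". For the Aim 2 endpoint, Section II says: "The primary outcome will be the average percent of glucagon calculated by the control algorithm that is successfully delivered by the pump". Its important secondary outcomes are glucagon-site reactions, nausea, glucagon exposure and "measures of glycemic regulation, including mean CGM glucose and hypoglycemia exposure (% time <60 mg/dl".

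Section X pays subjects for three visits but caps lunches at $100 "per subject (50 dollars per lunch"). It then adds, without a limit on number, that study funds will cover subjects' lunches.

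**The concern.** A rule written for two visits sits in a section that governs three. The natural two are the randomized Aim 1 pair, which leaves the Xeris visit as the one without a same-meal requirement. That visit is one side of every Aim 2 paired difference.

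Lunch matters to some of these outcomes. Section I.b says that glucagon dosing depends on the glucose level and its rate of descent. Section V.d.4 has every lunch announced as typical, so the announcement does not tell the controller about differences in content within that range. Exercise follows about two hours later. A different lunch could change post-meal glucose, the approach to hypoglycemia during exercise and the amount of glucagon requested.

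At stake is how cleanly the Aim 2 glycemic and exposure comparisons can be read with up to 10 subjects. Section VI.d adds a second reason for care. It counts the absence of a statistical difference in nausea, among other safety outcomes, as success for Xeris, and extra noise makes that easier to observe.

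**Working it through.** **1. Count of visits against the rule.**

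- Visits per subject in Section V.d.4: 3.
- Visits named in the lunch-matching rule: 2.
- Compensation in Section X: $150 at $50 per completed day, so 150 / 50 = 3 visits.
- Blood loss in Section V.d.4: about 360 ml in total at about 120 ml per visit, so 360 / 120 = 3 visits.
- Lunch allowance in Section X: 100 / 50 = 2 lunches.

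The matching rule and the lunch cap are written for two; the other counts are three. No other section extends the match to the third visit. Section II says for Aim 2 only that subjects fast until lunch. The infusion set sub-study (Section V.d.5) also asks for the same meal at both of its experiments, and there the count is right because there are two.

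**2. What still applies at the Xeris visit.** These rules in Section V.d.4 carry no limit on visits: fasting from midnight, a start no later than 9:00 AM, lunch after about 3-4 hours of closed loop, the usual carbohydrate range, the typical announcement, no carbohydrate intake after lunch, and exercise about two hours after it. What depends on the word *both* is that the meal is the same and that its timing is matched more closely within the 3-4 hour window.

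**3. Share of the visit after lunch.** With lunch at hour 3 or 4 of an 8-hour visit, the later share is (8 - 3)/8 = 62.5% or (8 - 4)/8 = 50%. Whole-visit measures such as mean CGM glucose therefore draw about half or more of their data from the period that lunch can influence.

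**4. Which Aim 2 outcomes lunch can reach.**

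- Primary outcome: glucagon delivered divided by glucagon calculated. Lunch may change the amount calculated, which is the denominator. The documents give no reason why it would change the fraction delivered.
- Glucagon-site reactions: no route from lunch is apparent.
- Mean CGM glucose, time below 60 mg/dl and glucagon exposure: reachable. Nausea: possibly.

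**5. The plan's own sample size.** Section VI.c gives 25, 10 and 8 subjects for Aim 1, with SD 2.5, 80% power and two-sided 5%. With n = 2(1.960 + 0.842)² × 2.5² / d²:

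- d = 98 - 96 = 2.0: 24.5, rounded up to 25.
- d = 99.2 - 96 = 3.2: 9.6, rounded up to 10.
- d = 99.6 - 96 = 3.6: 7.6, rounded up to 8.

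All three reproduce. The calculation concerns Aim 1 pump availability and does not involve lunch. No power calculation is given for Aim 2.

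**6. Size, as an illustration only.** The documents give no variance for the meal effect. Suppose unmatched lunches add a fraction k to the variance of a paired difference with n = 10. The standard error is then multiplied by √(1 + k). Take a true difference that has 80% power in a two-sided 5% paired t-test when k = 0:

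| k (assumed) | SE factor | Power |
|---|---|---|
| 0 | 1.00 | 80% |
| 0.25 | 1.12 | 71% |
| 0.50 | 1.22 | 63% |
| 1.00 | 1.41 | 51% |

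The table shows what each assumption would imply. It does not estimate k, which could be close to zero if subjects repeat their lunch anyway.

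**The case against.** The best defense is that this is a wording slip with visible intent. The sentence after the rule speaks of the same lunch without counting visits, and nothing in the plan requires or predicts a different third meal. The general rules in step 2 already bound the timing, carbohydrate and announcement at every visit. Section VI.a.2 records the time, content and carbohydrate amount of the meal, so a mismatch would be visible. The lunch cap is weak evidence, since Section X also says that lunch costs are covered.

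Most of this stands, and it limits the point. It does not remove it. The follow-on sentence explains the two-visit rule and does not widen it. A recorded mismatch would be hard to adjust for with at most 10 pairs. Staff who follow the text literally need not repeat the meal.

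A reader might go further and infer that the Aim 2 comparison is confounded by lunch. The documents do not support that. They permit a different lunch but do not impose one; the primary outcome is a device ratio; and unsystematic differences add variance without direction. Bias would need a systematic change in lunch at the third visit, and nothing in the plan points to one. If one did occur, the fixed third position of the Xeris visit would make it inseparable from period. That fixed order is a separate and larger weakness, which this correction would not cure.

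**Conclusion.** The inconsistency is real and sits in an operative procedure: three visits, and a matching rule for two. Its reach is limited to the meal-sensitive secondary outcomes of Aim 2, and to subjects who do eat differently at the Xeris visit. The consequence is possible added noise, or bias if the third lunch differs systematically.

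The Aim 2 primary outcome, Aim 1 and the stated sample sizes are not shown to be affected. The size of the effect cannot be derived from the documents; the figures in step 6 rest wholly on assumed values of k. The conclusion assumes that *both* refers to the two randomized Aim 1 visits, which is the ordinary reading but is not spelled out. The correction is worth making because it is specific and nearly free.

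**What to change.** In Section V.d.4, Visit Procedures, make the lunch rule refer to all three bionic pancreas visits, for both meal content and approximate time. In Section X, reconcile the lunch cap with three visits, either by raising it to 3 × $50 = $150 or by relying on the general statement that lunches are covered.

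The cost is a short wording change and at most one more lunch per subject: $50 each, or 10 × $50 = $500 for 10 completers. No endpoint, test or sample size changes.

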This sub-study is designed to isolate the performance of the modified iLet infusion set, and is a necessary step towards continuing human experiments using the iLet Bionic Pancreas. The study will consist of two 5-hour study visits in random order: one with an FDA approved 6 mm steel cannula (Contact Detach) luer-lock compatible infusion set and one with the investigational steel cannula luer-lock compatible infusion set developed for use with the iLet Bionic Pancreas.

III. Subject Selection

III. a. Inclusion Criteria

- Age ≥ 18 years and have had clinical type 1 diabetes for at least one year
- Diabetes managed using an insulin pump for ≥ 6 months
- Prescription medication regimen stable for > 1 month (except for medications that will not affect the safety of the study and are not expected to affect any outcome of the study, in the judgment of the principal investigator)
- Infusion Set Sub-Study:
 - Age ≥ 18 years
 - Type 1 diabetes for at least one year
 - Diabetes managed using an insulin pump

No subjects will be excluded on the basis of gender or race. The requirement that subjects manage their diabetes using subcutaneous insulin infusion pump therapy is imposed because multiple daily injection therapy involves the use of medium-acting or long-acting basal insulin that would require an extended washout period.

III. b. Exclusion Criteria

- Unable to provide informed consent (e.g. impaired cognition or judgment)
- Unable to safely comply with study procedures and reporting requirements (e.g. impairment of vision or dexterity that prevents safe operation of the bionic pancreas, impaired memory, unable to speak and read English)
- Current participation in another diabetes-related clinical trial that, in the judgment of the principal investigator, will compromise the results of this study or the safety of the subject
- Pregnancy (positive urine HCG), breast feeding, plan to become pregnant in the immediate future, or sexually active without use of contraception
- Current alcohol abuse (intake averaging > 3 drinks daily in last 30 days), use of marijuana within 1 month of enrollment, or other substance abuse (use within the last 6 months of controlled substances other than marijuana without a prescription)
- Unwilling or unable to refrain on the study days from:
 - acetaminophen in any form
 - use of marijuana

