Yellow Springs Instrument (YSI) 2300 STAT PLUS: The YSI Model 2300 STAT PLUS Glucose and Lactate Analyzer is a laboratory instrument that is intended for use in clinical care. It provides quick measurements of glucose in whole blood, plasma or serum and will be used as to measure plasma glucose during the visit. This device will be stored at the Diabetes Research Center when not in use, and study staff will follow proper maintenance and quality assurance procedures.

Exercise bike: the study will utilize a stationary exercise bike (ergometer) for the exercise portion of the visit. This bike will be stored at the Diabetes Research Center when not in use.

V.c.4. Infusion Set Sub-Study devices:

The Infusion set sub-study will use the following devices:

Infusion sets: The Infusion Set Sub-Study will use two different infusion sets. One will be the FDA approved Contact Detach, which is leur-lock compatible and uses a 29 gauge 6 mm steel cannula. This will be compared with the leur-lock compatible infusion set designed for use with the iLet Bionic Pancreas, that also uses a 29 gauge 6 mm steel cannula.

Insulin pump: subjects will wear their own leur-lock compatible insulin pump, or will be switched to a study provided leur-lock compatible infusion pump for the duration of the experiment.

Yellow Springs Instrument (YSI) 2300 STAT PLUS: The YSI Model 2300 STAT PLUS Glucose and Lactate Analyzer is a laboratory instrument that is intended for use in clinical care. It provides quick measurements of glucose in whole blood, plasma or serum and will be used as to measure plasma glucose during the visit. This device will be stored at the Diabetes Research Center when not in use, and study staff will follow proper maintenance and quality assurance procedures.

V. d. Experimental Procedures and Data Collection

V. d. 1. Screening Visit

- All subjects will have a screening visit to confirm eligibility. The subject will be interviewed and the case report form will be completed by study staff to establish whether the subject is eligible.
- A urine pregnancy test will be performed in female volunteers. If the test is positive the volunteer will be informed of the result and the visit will be ended.
- Height, weight and blood pressure will be measured.
- Blood will be drawn for hemoglobin A1c. Plasma fractionated metanephrines may be obtained if indicated by history.

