- We will tell subjects, both verbally and through an email that we will send them on the eve of their participation, that they are expected to take carbohydrates if needed to treat hypoglycemia, or indeed to avoid impending hypoglycemia, even if they are fasting. Furthermore, we will tell them that if they anticipate problems in the period between the time that they wake up and the time that they will arrive at the Diabetes Research Center for the start of the experiment, that they are encouraged to set a lower temporary basal rate on their pumps.
- We will remind subjects, both verbally and through an email that we will send them on the eve of their participation, that they are expected bring all of their diabetes management supplies that would normally use to manage their diabetes, including their own insulin pump, a vial of the specific insulin analog they use, a spare reservoir, at least two spare infusion sets, a glucometer, glucose strips, lancets, glucose tabs/juice, and a continuous glucose monitor if they have one. These supplies will in any case be needed at the end of the study period for re-initiation of their own pump therapy before they leave the Diabetes Research Center.
- If a subject arrives on the morning of a visit with a BG of >300 mg/dl, the experiment will not be initiated on that day and will be rescheduled. A study physician will evaluate the subject, provide assistance to the subject in bringing their BG back towards the target range, and make sure that they are medically safe before they leave.
- If the participating subject is hypoglycemic at any time after arrival, they will be treated with oral carbohydrates (15 g every 15 minutes until their BG is >70 mg/dl), and the study will start as normal.
- In the case of severe hypoglycemia that occurs before the study start, the experiment will not be initiated, and the principle investigator will determine whether the study visit should be re-scheduled or whether the participation of the subject should be ended. The subject's own physician will be informed of any severe hypoglycemic event.

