- A urine pregnancy test will be performed in female volunteers. If the test is positive the volunteer will be informed of the result and the visit will be ended. The date of the last menstrual period will also be documented, along with usual cycle length, for female subjects.
- Study staff will review any changes in medical history or medications since the last study visit, and obtain an updated medication list. Their current pump settings, including basal rates, carbohydrate ratios and correction factor will be documented.
- A 20 gauge or smaller peripheral I.V. will be placed for monitoring plasma glucose and insulin levels.
- Subjects will be provided with the rapid-acting insulin they usually use.
 - For subjects wearing their own leuc-lock compatible pump, a new reservoir will be filled with insulin lispro, new tubing will be primed and a new infusion set will be placed (either Contact Detach or iLet infusion set). The cannula will be primed as recommended by the manufacturer.
 - For subjects using the study provided pump, their pump settings will be programmed into the study pump. A new reservoir will be filled with insulin lispro and new tubing will be primed. A new infusion set (either Contact Detach or iLet infusion set) will be placed. The cannula will be primed as recommended by the manufacturer.
- A t=0, baseline plasma samples will be drawn for insulin levels, and a baseline blood glucose level will be obtained.
- Subjects will remain fasted for 90 minutes, while their pump (or the study pump) delivers their usual basal rate for this time of day. Non-caloric beverages and black coffee will be allowed.
 - During this time, blood will be drawn from the IV for plasma glucose levels at least every 30 minutes. Blood will be drawn more frequently as needed for hypoglycemia.
 - During this time, Blood will be drawn for plasma insulin levels every 30 minutes.
- A t=90, a 0.1 u/kg dose of insulin will be administered through the pump. Subjects will eat a breakfast of their choice containing carbohydrates appropriate to the insulin dose based on their own carbohydrate ratio and correction factor.
 - After breakfast is completed, subjects will not dose any further insulin and will resume fasting

until the experiment is completed.

- For 2 hours after the insulin injection (t=90 to t=210), blood will be drawn for plasma glucose and plasma insulin levels every 20 minutes.

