 - Blood will be drawn for plasma insulin levels then every 30 minutes thereafter until the end of the experiment.
- For the last hour and a half (from 2 to 3.5 hours after injection, t=210 to t=300), blood will be drawn for plasma glucose at least every 30 minutes and for plasma insulin levels every 30 minutes.
- The infusion set site will be assessed for pain, skin reactions, and evidence of failure immediately after insertion, at 1 hour intervals during the experiment, and at the end of each experiment. The participant will complete a short survey evaluating the user experience related to the infusion set at the end of the experiment.
- Three and a half hours after the meal bolus has been given the experiment will end (t=300). The IV will be removed, subjects will switch back to the usual infusion set (and/or pump if applicable) and they will be discharged. Subjects will be advised by a study provider on re-initiation of their own insulin regimen.
- Their basal rates, insulin dose and meal will be the same during both experiments.
- Hypoglycemia will be treated with oral carbohydrates as needed.

V. d. 6. Response to Hypoglycemia

- Subjects are encouraged to check their BG for any symptoms of hypoglycemia.
- Subjects will be permitted to take 15 grams of carbohydrates for any capillary BG value less than 60 mg/dl. Study staff will ensure proper functioning of the bionic pancreas and infusion set, and will encourage the subject to wait for the bionic pancreas to treat the low blood sugar for as long as they feel comfortable.
- Subjects will be required to take 15 grams of carbohydrates for any plasma BG value less than 50 mg/dl. Blood glucose will continue to be checked every 15 minutes per protocol, with increased frequency during exercise. Treatment will be repeated if subsequent BG values are still < 50 mg/dl after 15 minutes. All carbohydrate treatments for hypoglycemia will be documented by study staff (amount and time).
- Study staff will check the infusion site and the bionic pancreas for normal operation any time hypoglycemia occurs. If there is any suspicion of infusion set malfunction, the site should be replaced. Study staff will check the bionic pancreas for any malfunction and correct any problems that are found.
- If no correctable fault is found, but there is doubt regarding the correct function of the bionic pancreas system, an entirely new backup bionic pancreas system may be started.

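### Does the clash over which insulin fills the pump in the infusion set sub-study put the Aim 4 comparison at risk?

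*Combined protocol and SAP*

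**What the plan says.** Section V. d. 5 (Infusion Set Sub-Study Visit Procedures) opens the pump set-up with a general line: "Subjects will be provided with the rapid-acting insulin they usually use". Two steps are nested under it. For a subject's own pump, "a new reservoir will be filled with insulin lispro, new tubing will be primed and a new infusion set will be placed". For the study pump, "A new reservoir will be filled with insulin lispro and new tubing will be primed". Both steps cover whichever of the two infusion sets is being tested that day.

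Section V.c.4 gives no third arrangement: "subjects will wear their own leur-lock compatible insulin pump, or will be switched to a study provided leur-lock compatible infusion pump". At 90 minutes, "a 0.1 u/kg dose of insulin will be administered through the pump". Section V. d. 5 also fixes what must match between visits: "Their basal rates, insulin dose and meal will be the same during both experiments".

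On who may enter, the sub-study inclusion criteria in section III. a ask for "Diabetes managed using an insulin pump" and name no analogue; the sub-study exclusions in section III. b name none either. Section V. b (Drugs) lists lispro as the only insulin the study administers. Section VI. a. 3 records the subject's usual pump insulin at screening and the analogue actually administered at the visits. Section VI. b. 1 sets the Aim 4 primary endpoint as the insulin area under the curve in the 3.5 hours after the bolus.

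**The concern.** Every sub-study subject falls under one of the two filling steps, and both say lispro. A subject whose usual insulin is something else is eligible, yet for that subject the general line and the filling step contradict each other. Such subjects are foreseeable: section V. d. 4 asks main-study subjects to bring "a vial of the specific insulin analog they use", and section V. d. 1 lets those subjects go on to Aim 4.

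The list of items held the same at both visits covers basal rates, dose and meal but does not mention the analogue. If staff followed the general line at one visit and the filling step at the other, that subject's difference in insulin area under the curve would carry a product difference as well as an infusion set difference. With up to 10 completers, no power calculation for the sub-study, and a success criterion in section VI. d based on finding no significant difference, stray variance would be unwelcome.

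**Working it through.** The plan gives no mean, standard deviation or margin for the Aim 4 endpoint, so there is no figure to reproduce. The check is logical, with one count.

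**Which instructions can be followed together**

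| Usual insulin | Line followed | Visit 1 | Visit 2 | Same analogue? |
|---|---|---|---|---|
| Lispro | Both agree | Lispro | Lispro | Yes |
| Not lispro | Filling steps | Lispro | Lispro | Yes |
| Not lispro | General line | Usual product | Usual product | Yes |
| Not lispro | One line at each visit | One product | The other | No |

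The contradiction is confined to the last three rows. The analogue differs within a subject only in the last row.

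**What each row does to the paired comparison**

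Write the area under the curve for subject *i* at a visit with infusion set *s* and analogue *k* as

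AUC = (subject level)_i + (set effect)_s + (analogue effect)_k + error.

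The paired difference, iLet set minus Contact Detach, is

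d_i = (set effect, iLet − set effect, Contact Detach) + (analogue effect, iLet visit − analogue effect, Contact Detach visit) + error.

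- First three rows: the analogue is the same at both visits, so the second bracket is 0.
- If the analogue (or how the assay reads it) acts as a multiplier instead, it scales both visits of a subject alike. It cannot create a difference where the sets perform equally.
- Last row: the second bracket is not 0. The order of the two sets is randomised in blocks of two (section V. d. 2), so a switch tied to visit number rather than to the set adds noise and does not favour one set on average. The filling steps name lispro for both sets, so the text gives no reason to tie the insulin to the set.

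**Does any text lead to the last row?**

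- The general line points to one usual product per subject, with no distinction between visits.
- The filling steps name one product, with no distinction between visits or sets.
- The bolus goes through the pump, so it is whatever is in the reservoir. That this line names no insulin adds no ambiguity.
- The list of matched items does not name the analogue, but it contradicts neither line.
- The visit field for the analogue administered fits either line, and would show a switch if one occurred.

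**How many subjects**

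Section IV. a gives up to 10 completers and up to 20 enrolled. Let *p* be the share whose usual insulin is not lispro. The documents do not give *p*, so it is taken over its whole range, 0 to 1:

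- completers affected: 10 × *p* = 0 to 10
- enrolled affected: 20 × *p* = 0 to 20

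These ranges only restate the ceilings. They are not evidence that any subject is affected.

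**The case for a change.** The best argument for acting is that the text is contradictory as it stands and cheap to mend. The protocol has no rule that specific steps override a general line. Reading the general line as a supply of insulin for after discharge is strained, because it sits in the set-up before time zero with the filling steps nested under it. Nor can the matched dose be assumed to include the product: section VI. a. 3 lists the analogue administered separately from the amount given for the meal. Extra noise would also make a finding of no significant difference easier to reach.

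The textual part stands. The general line and the filling steps cannot both hold for a subject who does not usually use lispro. The lispro-only Drugs section agrees with the filling steps, which suggests a drafting slip somewhere, but it does not formally settle the matter.

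The consequence does not stand. It needs staff to change reading between one subject's two visits, which no section describes or invites. The point about noise and the success criterion applies only in that case. Adding the analogue to the matched items would write down what either line already produces.

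**Conclusion.** No change to the design, endpoint or analysis follows. The inconsistency is genuine but editorial: section V. d. 5 gives two insulin instructions that conflict for any subject not usually on lispro. The general line, the two filling steps and the Drugs section must be reconciled by the sponsor so that they agree. No view is taken here on which insulin is right.

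The expected effect on the Aim 4 paired comparison is nil if either line is applied consistently within a subject. The number of subjects for whom the wording matters is unknown, from 0 to 10 completers. No size can be put on the effect of a within-subject switch, because the documents give no variance for the endpoint, and none is claimed.

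This rests on one assumption: that staff use the same reading at both of a subject's visits. Each line taken alone leads to that, and the analogue recorded at the visits allows it to be checked.
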